For Aim 1 (cross-sectional study), we plan to enroll four groups of 40 subjects each: healthy controls, patients with OSA alone, patients with DM alone, and patients with DM+OSA. All four groups will be matched for age, gender, and body mass index (BMI), as well as duration of DM where appropriate.

For Aim 2 (randomized controlled trial), we plan to enroll 55 patients with DM+OSA. Data for all of these patients will be included in Aim 1, with additional data to be collected for Aim 2.

Inclusion Criteria

All patients: ≤70 years of age, weight ≤450 pounds (the maximum supported by the cardiac magnetic resonance (CMR) imaging table).

OSA patients: Respiratory disturbance index (RDI) ≥10 and <100 events/hour determined during two consecutive home sleep studies; no evidence of non-OSA sleep disorders, Epworth Sleepiness Scale (ESS) score ≤18 (/24) indicating normal/moderate daytime sleepiness levels, no history of motor vehicle accident/s or near-miss accident/s related to sleepiness within the previous two years; not a commercial driver; naïve to CPAP treatment; not currently receiving treatment of any kind for OSA.

DM patients: A clinical diagnosis of type 2 DM; glycated hemoglobin (HbA1c) <8.0% indicating stable glycemic control.

Healthy controls: Normal fasting plasma glucose (<100 mg/dl); RDI<10 events/hour determined during two consecutive home sleep studies; no evidence of any other sleep disorder/s.

Exclusion Criteria

All patients: Hematocrit <32, metallic implants or other contraindication of CMR; pregnancy; collagen vascular disease; hepatic or renal disease; cardiopulmonary disease; use of medications that could affect sleep/breathing, or that could interact with nitroglycerin, non-English speakers.

Briefly describe study procedures. Include any local site restrictions, for example, “Subjects enrolled at Partners will not participate in the pharmacokinetic portion of the study.” Describe study endpoints.

The study procedure for Aim 1 (visits 1-2) will be the same for all four subject groups (healthy controls, OSA patients, DM patients, OSA+DM patients). Patients enrolling in Aim 2 will first complete Aim 1 (visits 1-2) followed by Aim 2 (visits 3-6).

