Eligible subjects will be randomized to the treatment arm (active CPAP) or placebo arm (sham CPAP) of the trial. All subjects will be given a device which can be set to sham CPAP, active CPAP, or auto-PAP. The devices are identical, and subjects will not be aware of the settings in their allocated device.

Those assigned to the active CPAP group will need to undergo a one-week titration procedure using auto-PAP in order to determine a therapeutic pressure for ongoing CPAP use; the device will be set to auto-PAP mode. Those assigned to the sham CPAP group will not need to undergo a titration; the device will be set to sham CPAP mode.

Time will be available for questions and troubleshooting, with emphasis placed on strategies to maximize adherence.

- *Visit 5: Beginning of Randomized Controlled Trial*

Location: BWH Ambulatory Clinical Center or BWH Clinical Trial Center

Time Required: Approximately 30 minutes

Staff Responsible: Co-investigator

All subjects will return after one week, when adherence data will be downloaded from each device.

Subjects who are to continue with sham CPAP will have their device returned to them with no changes, although they will not be aware as to whether the mode of treatment has been changed. Subjects assigned to the active treatment group will also have pressure information downloaded from their device. A co-investigator will analyze these data and decide on a suitable fixed CPAP pressure. The mode of the device will be changed to active CPAP at this pressure, but again, the subjects will not know whether the settings of the device have been changed.

Time will be available for questions and troubleshooting, with emphasis placed on strategies to maximize adherence.

Subjects will use their sham / active CPAP devices for the next three months at home. During this time, subjects will attend face-to-face meetings with an unblinded co-investigator as required and/or requested by the subject. Subjects will perform regular blood sugar checks as needed. It may be necessary for some subjects to undergo an additional home-based sleep study while using active or sham CPAP; advice will be sought by a licensed physician.

- *Visit 6: End-Trial Vascular Testing & Cardiac MRI*

Locations: BWH Ambulatory Clinical Center or BWH Clinical Trial Center (early morning), BIDMC Microcirculation Laboratory (mid-morning), BIDMC MRI Laboratory (late morning), BWH Shapiro Cardiovascular Center (early afternoon)

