Official Title: Vascular Impairment in Type II Diabetes Mellitus with Co-morbid Obstructive Sleep Apnea

ClinicalTrials.gov ID (NCT number): NCT01629862

Statistical Analysis Plan Date: 01/05/2018

For the cross-sectional analysis of those with diabetes, sleep apnea, both, or neither, we will first use analysis of covariance to determine whether there is any interactive effect of sleep apnea and diabetes on our primary outcome (flow mediated dilation) as well as the three secondary outcomes (nitroglycerin-induced dilation, acetylcholine-induced skin blood flow, and sodium nitroprusside-induced skin blood flow) after controlling for age, sex, and body mass index (BMI). If a significant interaction is identified, the main effects of diabetes, sleep apnea, and their interaction will be reported using multivariable linear regression adjusting for age, sex, and BMI. If the interactive effect of sleep apnea and diabetes is not significant ($\alpha=0.05$), we will ignore any interaction and examine the additive effects of diabetes and sleep apnea on each outcome using multivariable linear regression adjusting for age, sex, and BMI. Using post-hoc contrasts, we will then further test for differences between those having both diabetes and sleep apnea alone versus those with diabetes alone and those with sleep apnea alone. All tertiary outcomes will be assessed in a similar fashion.

For the randomized clinical trial analysis, the primary outcome is percent change in flow mediated dilation (post-treatment minus pre-treatment divided by pre-treatment) with percent change in nitroglycerin induced dilation, acetylcholine induced skin blood flow and sodium nitroprusside induced skin blood flow as secondary outcomes. The primary analysis will be based on the use of unpaired t-tests to compare each outcome in those randomized to CPAP versus sham-CPAP using an intention to treat principle and $\alpha =0.05$. All tertiary outcomes will be assessed in a similar fashion. If significant differences ($\alpha =0.05$) are identified in key covariates (age, sex, BMI) between those randomized to CPAP and sham CPAP, secondary analyses will adjust for those covariates that significantly differ.

For all analyses, we will also report effect sizes with 95% confidence intervals to establish the size of our effects of interest.

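### The RCT's only adjusted analysis depends on baseline significance tests between randomised arms, so about 86% of trials would produce no adjusted estimate

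*SAP*

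**What the plan says.** The SAP's paragraph on the randomised trial defines the outcome this way: "the primary outcome is percent change in flow mediated dilation (post-treatment minus pre-treatment divided by pre-treatment". It then states: "The primary analysis will be based on the use of unpaired t-tests to compare each outcome", by intention to treat at alpha 0.05. Adjustment comes in only through a conditional rule. If a significant difference at alpha 0.05 is found "in key covariates (age, sex, BMI) between those randomized to CPAP and sham CPAP, secondary analyses will adjust for those covariates that significantly differ".

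No other part of the SAP or protocol gives an adjusted model for the trial. Tertiary outcomes are to be handled likewise, and effect sizes with 95% confidence intervals are promised for all analyses, but neither statement adds an adjusted model. Dividing by the pre-treatment value does not adjust for age, sex or BMI.

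The SAP's cross-sectional paragraph (Aim 1) adjusts the same vascular measures for the same three covariates without any preliminary test.

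Allocation is random (Protocol, Visit 4): "Eligible subjects will be randomized to the treatment arm (active CPAP) or placebo arm (sham CPAP) of the trial". On size, the protocol's Research Design and Methods section says: "we plan to enroll 55 patients with DM+OSA".

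**The concern.** Because the arms are randomised, a significant baseline difference arises by chance. Adjustment is useful when a covariate predicts the outcome, and the p-value for a between-arm difference does not measure that. The rule therefore selects on the wrong quantity and will usually withhold the adjusted analysis.

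Analyst discretion is not the issue, since the candidate covariates, the alpha and the trigger are all fixed in advance. The issue is what the trigger does. In a trial of about 55 subjects, readers will predictably ask whether chance imbalance in age, sex or BMI explains the result. Under this plan there will usually be no prespecified adjusted estimate to answer them. Robustness is at stake and, if the covariates are prognostic, so is precision in a secondary analysis.

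**Working it through.** The documents give no figure on this point, so there is none to reproduce.

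**Inputs**
- SAP: three covariates, each tested at alpha 0.05 (two-sided assumed).
- Protocol: 55 planned. The allocation ratio is not stated, so 27 v 28 is assumed. Subjects who do not tolerate the mask are excluded before randomisation, so 20 v 20 is shown as a lower case.
- Not in the documents: R², the share of variance in percent change explained by age, sex and BMI together. Values of 0, 0.1, 0.2 and 0.3 are shown.

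**1. How often the rule fires (independent tests)**
- No covariate significant: 0.95³ = 0.857.
- Exactly one: 3 × 0.05 × 0.95² = 0.135.
- Exactly two: 3 × 0.05² × 0.95 = 0.0071.
- All three: 0.05³ = 0.000125.

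When the rule fires, it adjusts for a single covariate in 0.1354/0.1426 = 95% of cases (92–96% in simulation). Simulations with arms of 28 v 27, 20 v 20 and 14 v 14, covariate correlations of 0 to 0.8, and a chi-square or Fisher exact test for sex put the no-adjustment probability at about 0.85 to 0.91.

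**2. Imbalance that goes unadjusted**
- Threshold for a continuous covariate: t(0.975, 53) × √(1/27 + 1/28) = 0.541 SD. At 20 v 20: t(0.975, 38) × √(2/20) = 0.640 SD.
- Probability that one such covariate differs by 0.3 SD up to the threshold: 0.221 (20 v 20: 0.299).
- Probability that age or BMI lies in that range and no test is significant: [0.95² − (0.95 − 0.221)²] × 0.95 = 0.35. At 20 v 20: [0.95² − (0.95 − 0.299)²] × 0.95 = 0.45. Simulation gives the same values.

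**3. Precision of a fixed model with age, sex and BMI**

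The standard error relative to the unadjusted analysis is about √[(1 − R²) × 53/50], which is 1.030, 0.977, 0.921 and 0.861 at R² = 0, 0.1, 0.2 and 0.3. At 20 v 20, √[(1 − R²) × 38/35] gives 1.042, 0.989, 0.932 and 0.872. Break-even with no adjustment is at R² = 1 − 50/53 = 0.057 (20 v 20: 1 − 35/38 = 0.079).

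**4. The rule against the fixed model**

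Simulation at 27 v 28, 40,000 trials per cell: no treatment effect, normal age and BMI, 60% of one sex, equal covariate contributions, uncorrected chi-square for sex. The first four rows are SDs of the estimate relative to no adjustment.

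| | R² = 0 | 0.1 | 0.2 | 0.3 |
|---|---|---|---|---|
| Rule, all trials | 1.008 | 0.996 | 0.980 | 0.964 |
| Fixed model, all trials | 1.030 | 0.978 | 0.921 | 0.861 |
| Fixed model, rule did not fire | 1.022 | 0.980 | 0.938 | 0.888 |
| Fixed model, rule did not fire, age or BMI imbalance of 0.3 SD or more | 1.038 | 0.981 | 0.903 | 0.853 |
| Share of the fixed model's SD reduction recovered when the rule fires | – | 0.71 | 0.74 | 0.75 |

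The last row at R² = 0.2, for example, comes from SDs of 0.303 (unadjusted), 0.269 (rule) and 0.257 (fixed): (0.303 − 0.269)/(0.303 − 0.257) = 0.74. A separate 30,000-trial run gave 0.68 (bootstrap 95% interval 0.48–0.85), 0.75 (0.70–0.81) and 0.72 (0.68–0.75). At 20 v 20 the shares are 0.56, 0.68 and 0.69. The R² = 0.1 values are imprecise.

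The type I error of the unadjusted t-test was 4.9–5.2% in every cell.

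**The case against.** The strongest reply is that nothing the trial's conclusion rests on is affected. The unadjusted intention-to-treat t-test is primary and valid, and when no significant imbalance appears the plan simply keeps it. This stands, and it limits the point to a secondary analysis.

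Second, the 86% measures how often the adjusted estimate is missing, not how much harm follows. Dividing the fixed-model row of the table by the rule row, the fixed model changes the SD by about +2%, −2%, −6% and −11% at R² = 0, 0.1, 0.2 and 0.3. A material gain therefore needs R² of about 0.2 or more, which no passage establishes. At R² = 0 the fixed model is slightly worse. This also stands. Likewise, the 0.3 SD cut-off behind the 35% is a reviewing choice, and an imbalance of that size matters only if the covariate is prognostic.

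Third, the evidence that these covariates matter is indirect. Aim 1 compares non-randomised groups, where adjustment addresses confounding, so treating the two aims differently is not a contradiction. The protocol's remark, under Equitable Selection of Subjects, that the OSA–control gap in endothelial function is hard to see after age 50 concerns a group contrast, not percent change under treatment. That is fair: these passages show the covariates are thought relevant to the vascular measures, not how much of the percent change they explain.

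None of this defends the trigger itself. Baseline significance remains the wrong basis for deciding whether to adjust.

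**Conclusion.** The concern holds, as a modest and cheaply corrected defect in a secondary analysis. The absence of an adjusted estimate in about 86% of trials follows from randomisation and three independent 5% tests and needs no assumption about R². Correlated covariates or an exact test for sex raise it, to at most about 91% in the cases tried. The loss lies mainly in trials where the rule does not fire. Where it does fire, it recovers roughly 70–75% of the fixed model's SD reduction at 27 v 28, and less at 20 v 20.

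The precision figures rest on assumed 1:1 allocation, equal covariate contributions and the R² range shown. There is no claim of bias or of false-positive inflation in the primary test. The change should be made, but the primary result does not depend on it.

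**What to change.** Delete the baseline-test trigger. In its place, prespecify one adjusted secondary (sensitivity) model for FMD and for each of the three secondary outcomes: percent change regressed on arm, age, sex and BMI, fitted whatever the observed balance and reported with its 95% confidence interval beside the unadjusted result. State that the unadjusted t-test remains primary.

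The cost is one sentence in the SAP. The covariates are already used in the Aim 1 models, and all trial participants are in Aim 1. The secondary model spends three of 53 residual degrees of freedom. If the covariates are not prognostic, its standard error is about 3% larger than the unadjusted one (4% at 20 v 20).
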